**Table 2 Terminology and Definitions cont.**

Terminology	Definition
Patient-Reported Outcome cont.	
 
• Diarrhea intensity
 
• Diarrhea frequency
 
• Fullness before finishing a meal (Early satiety) intensity
 
• Loss of appetite intensity
 
• Bloating intensity
 
• Abdominal cramping intensity
 

	Each intensity evaluation is scored on a scale of 0=none to 10=worst possible.
Prior Medication	Medication collected on the Prior/Concomitant Medication CRF, with start date prior to Study Day 1.
PRO Total Symptom Score	Total symptom score (TSS) is the sum of 6 (abdominal pain, abdominal cramping, bloating, nausea, early satiety, and loss of appetite) weekly average symptom intensity scores.
Study Day	Study Day 1 is defined as the date on which a subject took the first dose of study drug. Other study days are defined relative to Study Day 1. For visits prior to the first dose of study drug, Study Day is calculated as Visit Date – Day 1 Date. For visits after the first dose, Study Day is calculated as Visit Date – Day 1 Date +1.
Study Drug	AK002 or placebo administered by IV infusion.
Study Week	Study Week for PRO analysis is defined as 7 days a week starting from the day of first dose (Day 1).
Tissue Eosinophil Responder in EoD	Mean duodenal eosinophil count $\leq$ 15 cells/hpf in 3 highest duodenal hpf.
Treatment-emergent	Adverse events reported in the clinical database with a date of onset on or after the start date of the first dose of the study drug.
Treatment Responder	Subject with >30% improvement in TSS from baseline and mean eosinophil count $\leq$ 15 cells/hpf in 3 highest duodenal hpf.

## 4.2 Target of Estimation

The estimand (target of estimation) for Protocol AK002-020 is:

*In subjects with EoD, what is the between group (AK002 vs. Placebo) difference in the proportion of tissue eosinophil responders at Week 24, and the group difference in TSS from baseline to Weeks 23–24 as measured by the patient-reported outcome (PRO) questionnaire.*

The sections below describe the attributes of the estimand consistent with the ICH E9 (R1) Addendum ([FDA, 2021](#)).

#### **4.2.1 Population Targeted by the Scientific Question**

The population targeted by the scientific question is defined via the inclusion and exclusion criteria as part of the study protocol. Subjects must have a histological diagnosis of EoD. A key aspect of eligibility is that subjects must have a weekly average score of abdominal pain, nausea, or diarrhea  $\geq 3$  on the PRO questionnaire (score from 0–10) for at least 2 weeks of screening and a weekly average TSS of  $\geq 10$  for at least 2 weeks of screening.

The protocol specifically excluded conditions including inflammatory bowel disease, other chronic inflammatory diseases in the colon (with the exception of eosinophilic colitis), celiac disease, achalasia, or esophageal surgery as these were identified at the time of study conception as potential confounders to interpretation of the degree of change in TSS based on overlap in symptomatology and several of the symptom-based components of the TSS PRO. The intent of this study criteria was as an exclusionary measure for any condition that may interfere with the interpretation of the assessment of efficacy based on the TSS instrument however the list of exclusionary conditions was not exhaustive and other concomitant conditions that could likewise confound interpretation and detection of a treatment effect may not have been fully appreciated (see exclusion criterion 7 and Appendix 5 in study protocol).

Subsequently, a supplementary analysis of data from a recent study, AK002-016, focused on identification of baseline characteristics which correlate with degree of change in TSS6 at Weeks 23-24. This examination identified eight variables (age, gender, duodenal eosinophil counts, diarrhea frequency, history of IBS, abdominal pain, esophageal eosinophils per hpf  $> 6$ , and history of IBS in combination with diarrhea intensity  $\geq 3$ ) that most influenced the degree of change of the TSS endpoint. Two of the variables (esophageal eosinophils per hpf  $> 6$ , and history of IBS in combination with diarrhea intensity  $\geq 3$ ) potentially reflect other disease states (IBS, GERD or even active EoE) that could potentially impact multiple symptom components of TSS6. To ensure these two variables do not compromise the capacity to detect the treatment effect with symptoms of EoD as measured by the TSS questionnaire, the primary comparison of AK002 vs placebo will be conducted on the Evaluable population defined as subjects who do not exhibit any of the following conditions at baseline:

1.  $> 6$  eosinophils per hpf in at least one esophageal site.
2. Documented history of irritable bowel syndrome and baseline diarrhea intensity  $\geq 3$ .

#### **4.2.2 Variables of Interest (or Endpoint) to be Obtained for Each Subject that is Required to Address the Scientific Question**

The co-primary endpoints to be obtained for each subject in this study to address the scientific question are **tissue eosinophil responders** (as defined in Table 2) at Week 24 and change in TSS from baseline to Weeks 23–24 as measured by the PRO questionnaire.

#### **4.2.3 Treatment**

AK002 or placebo administered to subjects on Days 1, 29, 57, 85, 113, and 141.

#### **4.2.4 Intercurrent Events**

The events below are considered intercurrent events (ICE) confounding with the efficacy outcomes.

- Premature discontinuation from the study
- Use of prohibited/restricted medication

Further clarification and handling of ICE including prohibited/rescue medications is detailed in [Appendix 2](#).

#### **4.2.5 Strategy for Handling Intercurrent Events**

For the analysis of the study product estimand, tissue eosinophil values and TSS will be counted as non-responders for binary variables and set to missing for continuous outcomes from the point when an ICE occurs. The estimand will provide an answer to the question that is crucial to individual subjects:

“If I take this study medication as part of my treatment regimen, without adding any further medications that may impact the underlying disease or exit the study prematurely, what improvements in histology and PRO symptoms might be anticipated after 24 weeks?”

#### **4.2.6 Summary Measure of the Estimand**

- Percent (and 95% CI) of subjects having tissue eosinophil response at Week 24 in the AK002 and Placebo treatment groups and the absolute difference (and 95% CI) in the percent response between treatments.
- Least squares mean (LSM) (and standard error [SE]) of change from baseline to the average of Weeks 23–24 TSS and the between treatment difference in the AK002 and placebo treatment groups LSM. LSM and SE derived from mixed model repeated measures (MMRM) model.

### **5. Statistical Methods**

#### **5.1 General Methodology**

All statistical analyses will be conducted using SAS v9.4 or later version on the Microsoft Windows Operating System.

All CRF data (raw data) will be converted into SDTM (Study Data Tabulation Model) datasets, which will be used to create ADaM (Analysis Data Model) data sets. The creation of the SDTM and ADaM data sets will follow the CDISC (Clinical Data Interchange Standards Consortium) standards and the FDA Study Data Technical Conformance Guide. All analysis tables and listings will be created from the ADaM data sets.

Continuous data will be summarized using “n” (number of subjects with non-missing observations), mean, median, standard deviation (SD), minimum value, and maximum value. Categorical data will be summarized using the frequency count and percentage (n, %) of subjects in each category. Number of subjects with non-missing values or number of subjects with missing values (e.g., Not Done) will be presented, where appropriate. Subjects with missing values will not contribute to the denominator for percentage calculations, unless specified otherwise. Counts of 0 in any category will be presented without percentage. All summaries will be presented for individual treatment groups. In addition, for summary of disposition and subject baseline characteristics, the presentation will include both treatment groups combined.

The precision rules for the presentation of summary statistics will be:

- Sample size (n, N) and number of missing responses (if displayed): Integer
- Mean, confidence interval, and median: Same number of decimal places as reported/collected
- Standard deviation: Same number of decimal places as reported/collected
- Percentiles, minimum, maximum: Same number of decimal places as reported/collected
- Odds Ratio: 2 decimal places
- Percentage: 1 decimal place generally, or 2 decimal places for <0.1%, or no decimal places for 0% and  $\geq 100\%$
- P-value: 4 decimal places
- WBC: 2 decimal places as  $0.01 \times 10^9/L$
- Height/Weight/BMI: 1 decimal place

The data summaries will be accompanied by individual subject data listings. All data available from questionnaires, eCRF, and external transfer (labs) will be listed and will include relevant subject information, e.g., treatment group and study day. The listings will be sorted in the order of treatment group, subject ID, assessment name and date/time.

Dates will be presented in the ISO-8601 format YYYY-MM-DD. Times will be displayed in 24-hour clock format. Numbering for tables, figures and listings will follow ICH E3 Guideline (ICH, 1996).

Alternative methods of analysis of the data may be considered prior to database lock should some of the assumptions underlying the proposed analyses not be met. Reason for departure from the planned methods will be documented as an amendment to the SAP or in the CSR.

## 5.2 Visit Window and Unscheduled Assessments

Data collected for study assessments provide information on the status of the subject at a given time point. These may provide biased results if the assessment is performed early or late. Therefore, assessments will be slotted into analysis windows to allow summaries to be performed for subjects with similar study drug exposure. The analysis window is constructed by the medians of 2 target study days of the adjacent planned visits.

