**Table 5 Analysis Window Rules for PK Concentration and ADA**

Visit Description	Window
Baseline	On or Prior to Day 1 Predose
Day 8	Day 1 Postdose to Day 11
Day 15	Day 12 to Day 22
Day 29	Day 23 to Day 42
Day 57	Day 43 to Day 70
Day 85	Day 71 to Day 98
Day 113	Day 99 to Day 126
Day 141	Day 127 to Day 154
Day 169	Day 155 to Day 172
Day 176	Day 173 to Day 186
Day 197	Day 187 to Day 210
Day 225	Day 211 to End of Study

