**Table 6 Analysis Window Rules for Blood Histamine and Urinalysis**

Visit Description	Window
Baseline	On or Prior to Day 1 Predose
Day 1	Predose on Day 1
Day 29	Day 1 Postdose to Day 42
Day 57	Day 43 to Day 70
Day 85	Day 71 to Day 98
Day 113	Day 99 to Day 126
Day 141	Day 127 to Day 158
Day 176	Day 159 to Day 186
Day 197	Day 187 to End of Study

In the event of multiple values from unscheduled or early termination assessments within a single analysis window, the value closest to the scheduled visit target study day will be used for analyses. If 2 values tie as closest to the time point (for example, 1 value is before and the other value is after the time point), then the later value will be selected. Data collected at all visits will be included in the data listings with visit presented as reported by the site.

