### 6.15.2 Laboratory Test

Laboratory data will be summarized by presenting summary statistics of raw data and change from baseline values (means, medians, standard deviations, ranges). For quantitative laboratory parameters, both actual values and change from baseline values will be summarized at each visit.

Shift tables will be presented, in which, lab test results at baseline and post-baseline visit will be classified into below ( $<\text{LLN}$ ), within ( $\geq\text{LLN}$  and  $\leq\text{ULN}$ ), and above ( $>\text{ULN}$ ) normal ranges. Subject incidences (n and %) will be presented for the shift from baseline to the post-baseline visits.

Note that the analysis window will be applied for the visits.

A complete laboratory data listing, including hematology, biochemistry, and urinalysis will be provided for all subjects.

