#### **6.15.3 Vital Signs, Height and Weight, and Other Safety Measures**

Vital signs will be summarized by presenting summary statistics of raw data and change from baseline values (means, medians, standard deviations, ranges) for each visit (per analysis window) and time point. A data listing will include vital signs from all visits.

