Table 14.3.1.8b	Treatment-Emergent Adverse Events of Special Interest by System Organ Class and Preferred Term: Subject Incidence (Evaluable Population)
Table 14.3.2.1	Hematology: Change from Baseline by Visit (Safety Population)
Table 14.3.2.2	Blood Chemistry: Change from Baseline by Visit (Safety Population)
Table 14.3.2.3	Hematology: Shift from Baseline Classification by Visit (Safety Population)

Table 14.3.2.4      Blood Chemistry: Shift from Baseline Classification by Visit  
(Safety Population)

Table 14.3.2.5      Urinalysis: Change from Baseline by Visit (Safety Population)

Table 14.3.3      Summary of Vital Signs by Visit (Safety Population)

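### SAP Table 4 departs from the SAP 5.2 midpoint rule: no Day 8, 169 or 225 row for laboratory tests, and no Day 225 row for vital signs

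*SAP*

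**What the plan says.** SAP 5.2 gives one construction rule for all windows: "The analysis window is constructed by the medians of 2 target study days of the adjacent planned visits". The median of two days is their midpoint.

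Table 4 serves vital signs and laboratory tests together. After Day 1 its rows are Days 15 (2–22), 29, 57, 85, 113, 141 (127–158), 176 (159–186) and 197 (187 onward). Table 5, for PK and ADA, also has Day 8 and Day 169 rows and closes with a Day 225 row, "Day 211 to End of Study". Table 6, for histamine and urinalysis, closes with Day 197, "Day 187 to End of Study".

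The selection rule below Table 6 begins "In the event of multiple values from unscheduled or early termination assessments within a single analysis window". It takes the value nearest the target day and, in a tie, the later one. The same paragraph protects the listings: "Data collected at all visits will be included in the data listings with visit presented as reported by the site".

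SAP 6.15.2 binds the laboratory summaries to these windows: "Note that the analysis window will be applied for the visits". SAP 6.15.3 summarises vital signs "for each visit (per analysis window) and time point"; 6.15.2 has no such split by time point.

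Protocol 11.2.5 and 11.5, and the SAP's own schedule, place CBC and chemistry on Days 8, 169 and 225. CBC is drawn twice on each dosing day, before the infusion and 1 hour after it. Protocol Table 2, note 3, places vital signs on Day 225.

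**The concern.** The windows exist so that each summary groups patients with similar exposure. As printed, Table 4 pools scheduled visits that the protocol keeps apart. Its last row takes in samples drawn 56 and 84 days after the last dose under one label, Day 197.

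Three things are at stake.

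- Day 8 is the first scheduled chemistry after the first infusion, because the Day 1 chemistry is predose. It has no row of its own.
- Where two scheduled values share a row, the SAP does not say which one enters the table. SAP section 7 requires two independently programmed versions to match, but here the text gives the programmers no common rule.
- Protocol 2.3 reports a short-lived fall in lymphocytes after infusion. The hematology summaries for Days 29 to 141 therefore depend on whether the predose or the postdose CBC is used.

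**Working it through.** **Inputs**

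- Laboratory target days after Day 1 (protocol 11.2.5, 11.5; SAP Table 1): 8, 15, 29, 57, 85, 113, 141, 169, 176, 197, 225. That is 11 visits, with ±2 days at Days 8 and 15 and ±3 elsewhere. Patients entering the open-label extension stop at Day 176, which leaves 9.
- Vital-sign target days after Day 1 (protocol Table 2): 15, 29, 57, 85, 113, 141, 176, 197, 225. That is 9 visits, or 7 for extension entrants.
- Rule (SAP 5.2): cut = (a + b)/2 for adjacent target days a and b.

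**Step 1. Reproduce Table 5.** PK has the same visit days after Day 1 as the laboratory tests. The cuts are (8+15)/2 = 11.5; (15+29)/2 = 22; (29+57)/2 = 43; (57+85)/2 = 71; (85+113)/2 = 99; (113+141)/2 = 127; (141+169)/2 = 155; (169+176)/2 = 172.5; (176+197)/2 = 186.5; (197+225)/2 = 211. These match every printed boundary from the end of the Day 8 row onward. A whole-number midpoint goes to the later row, except Day 22, which stays with Day 15.

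**Step 2. Test Table 4.** Its cuts at 22, 43, 71, 99 and 127 agree. The next cut is 158/159, which is (141+176)/2 = 158.5 and skips the Day 169 laboratory visit. The cut at 186.5 agrees, and the table then stays open-ended. So Table 4 is what the rule gives for the vital-sign schedule cut short at Day 197. Its Day 15 row also starts at Day 2, although (1+15)/2 = 8.

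**Step 3. Place on-time laboratory visits in Table 4.**

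| Visit | On-time days | Row it falls in | Days from that row's target | On-time neighbour's distance |
|---|---|---|---|---|
| Day 8 | 6–10 | Day 15 (2–22) | 5–9 | 0–2 |
| Day 169 | 166–172 | Day 176 (159–186) | 4–10 | 0–3 |
| Day 225 | 222–228 | Day 197 (187 on) | 25–31 | 0–3 |

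Day 225 vital signs behave like the last line.

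**Step 4. Count.** Visits without their own row:

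- Laboratory: 3 of 11 (Days 8, 169, 225); 2 of 9 in extension entrants.
- Vital signs: 1 of 9 (Day 225); 0 of 7 in extension entrants, who have no Day 225 visit.

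**Step 5. Rows with two scheduled values and no stated choice.**

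- Chemistry: Days 15, 176, 197.
- CBC: the same three, plus Days 29, 57, 85, 113 and 141 (predose and 1 hour postdose).
- Vital signs: Day 197.

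**Step 6. Conditional check.** If the nearest-value rule were extended to on-time scheduled visits, the neighbour would win in all 5×5 = 25 day combinations for Day 8 against 15, in all 7×7 = 49 for Day 169 against 176, and in all 49 for Day 225 against 197. If the tie rule were extended too, two CBCs on the same study day would resolve to the later, postdose count.

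**Step 7. Urinalysis.** Protocol 12.16 lists it at Day 225 and the schedule marks it there. Protocol 11.5.2 and note 25 name only screening, Day 29, early termination and symptom-based samples. If it is collected at Day 225, it falls in the Day 197 row of Table 6, where no other urinalysis is scheduled. The midpoint of Days 29 and 225 is 127, so Table 6, with rows for Days 57 to 197, was not built from the urinalysis schedule.

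**The case against.** The strongest reply is that Table 4 still works. Every postdose date falls in exactly one row. Chemistry is drawn once per dosing visit, so its Day 29 to 141 rows are unambiguous. Vital signs are already split by time point, and only their Day 197 row holds two scheduled visits. Protocol section 15 makes no formal inference on safety, and the listings keep each value under the site's own visit label. SAP 5.1 also allows documented changes before database lock.

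Most of this stands, and it limits the point. It does not remove the conflict between the stated rule and the printed table. Table 5 shows that the SAP applies the rule in full to the same visit days, and no reason is given for treating the laboratory tests differently.

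Some stronger readings are tempting but unsupported.

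- A reader might infer that the by-visit safety tables as a whole cannot be reproduced. Only the rows in Step 5 lack a rule.
- A reader might infer that Day 8, 169 and 225 values are always discarded. That assumes a selection rule which the SAP does not state for scheduled values.
- A reader might infer that Day 225 urinalysis is lost as well. It has no scheduled Day 197 competitor, so only its label is wrong, and whether it is collected then is itself inconsistent.

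**Conclusion.** The point holds. For laboratory tests, Table 4 contradicts the rule that SAP 5.2 says produced it. For vital signs it omits a planned visit. Scheduled values are pooled with a neighbour without a stated choice or, if the neighbour is missing, reported under the wrong visit.

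The size is modest. The gap covers 3 of 11 laboratory visits and 1 of 9 vital-sign visits, with the Day 225 part confined to patients who do not enter the extension. Five CBC dosing-day rows also hold two scheduled draws. Five planned tables are affected (14.3.2.1 to 14.3.2.4, and 14.3.3). Table 14.3.2.5, urinalysis, has at most a labelling problem. Adverse event summaries, listings and efficacy results do not change.

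The counts assume visits within their protocol windows and leave early termination visits out. The correction should be made before database lock because the table is wrong as written and the change is cheap.

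**What to change.** In SAP 5.2, give laboratory tests their own table:

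- Day 1: postdose, as now.
- Day 8: 2–11. The Day 2 start keeps Table 4's convention; the strict Day 1/Day 8 midpoint is (1+8)/2 = 4.5. No on-time visit is affected.
- Day 15: 12–22.
- Days 29 to 113: unchanged.
- Day 141: 127–154.
- Day 169: 155–172.
- Day 176: 173–186.
- Day 197: 187–210.
- Day 225: 211 to end of study.

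Every on-time laboratory visit then falls in its own row. For vital signs, end the Day 197 row at Day 210 and add Day 225 from Day 211.

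Extend the selection rule to scheduled values, applied within each time point. It is still needed with the new rows: a Day 169 visit held late, on Day 173, falls in the Day 176 window. In 6.15.2, summarise predose and 1-hour postdose CBC as separate time points.

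For urinalysis, first reconcile protocol 12.16 and the schedule with 11.5.2 and note 25. If a Day 225 sample is collected, label it Day 225 in Table 6.

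The cost is SAP wording and a few more table rows. No new samples are needed for the laboratory and vital-sign changes.

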**Table 3 Analysis Window Rules for CCI**

Visit Description	Window
Baseline	On or Prior to Day 1 Predose
Day 1	Predose on infusion Day 1
Day 29	Day 1 Postdose to Day 42
Day 57	Day 43 to Day 70
Day 85	Day 71 to Day 98
Day 113	Day 99 to Day 126
Day 141	Day 127 to Day 158
Day 176	Day 159 to Day 186
Day 197	Day 187 to End of Study

**Table 4 Analysis Window Rules for Vital Sign and Laboratory Tests**

Visit Description	Window
Baseline	On or Prior to Day 1 Predose
Day 1	Day 1 Postdose
Day 15	Day 2 to Day 22
Day 29	Day 23 to Day 42
Day 57	Day 43 to Day 70
Day 85	Day 71 to Day 98
Day 113	Day 99 to Day 126
Day 141	Day 127 to Day 158
Day 176	Day 159 to 186
Day 197	Day 187 to End of Study

**Table 5 Analysis Window Rules for PK Concentration and ADA**

Visit Description	Window
Baseline	On or Prior to Day 1 Predose
Day 8	Day 1 Postdose to Day 11
Day 15	Day 12 to Day 22
Day 29	Day 23 to Day 42
Day 57	Day 43 to Day 70
Day 85	Day 71 to Day 98
Day 113	Day 99 to Day 126
Day 141	Day 127 to Day 154
Day 169	Day 155 to Day 172
Day 176	Day 173 to Day 186
Day 197	Day 187 to Day 210
Day 225	Day 211 to End of Study

**Table 6 Analysis Window Rules for Blood Histamine and Urinalysis**

Visit Description	Window
Baseline	On or Prior to Day 1 Predose
Day 1	Predose on Day 1
Day 29	Day 1 Postdose to Day 42
Day 57	Day 43 to Day 70
Day 85	Day 71 to Day 98
Day 113	Day 99 to Day 126
Day 141	Day 127 to Day 158
Day 176	Day 159 to Day 186
Day 197	Day 187 to End of Study

In the event of multiple values from unscheduled or early termination assessments within a single analysis window, the value closest to the scheduled visit target study day will be used for analyses. If 2 values tie as closest to the time point (for example, 1 value is before and the other value is after the time point), then the later value will be selected. Data collected at all visits will be included in the data listings with visit presented as reported by the site.

